Objective 3: Interviews will be conducted with 25-40 family members and 15-20 couples who participate in at least one storytelling session four months after enrollment. We will recruit family members of at least 10 different couples to ensure we have enough variability. We will complete interviews until we reach data saturation[77]. In this population, data saturation has been reached after an average of 30 interviews; thus, we hope to reach saturation with this sample.

e. Sampling

1. [Objectives 1-2] Participants: Eligible discordant couples will be enrolled at the study site on a first come, first enrolled (consented) basis until 70 couples have been enrolled. Randomization will be done using Stata with the results printed into numbered envelopes opened by the study assistant at the time of participant enrollment.
2. [Objectives 3] Participants: For qualitative in-depth interviews with family members, we will use convenience sampling to identify family members of couples who were successful and those who were unsuccessful at adhering to PrEP/ART.

f. Recruitment procedures

Serodiscordant couples identified in ANC will be informed about their eligibility for a study by the maternal and child health nurse. If the couple is interested in discussing further, they will be referred to a study assistant based at the health facility. This study assistant will sit with both members of the couple to describe the study. The specific points they will address include (but are not limited to), (1) that if the participants are randomized to the intervention group we will include them and their nominated family members in three storytelling sessions to increase understanding and support for use of PrEP and ART medications; (2) that some people are randomized to the control group, which means that they will receive the normal PrEP and HIV care and treatment at the health facility; (3) that we will measure the female's PrEP adherence using a point of care urine test at each medication pick up for the first three months on the PrEP regimen. The couples will be offered to ask any questions and will be explained that their participation is voluntary. If the both members of the couple consent to participate, they will be randomized to the control or intervention group using a pre-determined allotment recorded within a sealed envelope at the health facility site.

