
Procedures for drug level measurement.

Every time the couple returns for a medication pick up the woman on PrEP will be asked to provide a small sample (1ml is sufficient) of urine for the tenofovir assay. If a participant misses a medication pick-up, or if their male partner picks up their medication, the study assistant will bring the urine assay to the participant's home to complete the test. The test is simple to use: like a pregnancy test, the patient only has to urinate on a testing stick to identify the presence of the medication.

Study procedures for the qualitative interviews

Qualitative interviews will be conducted at least 4 months after the couple and their indicated family members have been enrolled in the study. We will purposely select roughly equal numbers of participants (including couples and their family members) who were adherent to PrEP/ART and those who have not been adherent to medication (measured via ART pick-ups and PrEP drug level assays). Interviews will be arranged by the study assistant and can be completed either at the health facility or at the home of the participant (depending on the preference of the participant). The qualitative interviews will only be completed one time, with no additional follow-up for the

participant.

Measurement of Results

Objective 1: Using interviewer assisted surveys, we will collect male and female partner (1) depression;[79] (2) partner and family support;[60, 80] (3) empathy;[81] (4) relationship satisfaction;[82] (5) PrEP adherence knowledge; and (6) motivation/perceived ability to adhere to medication[83] at baseline and three months.

Objective 2: Routinely collected demographic, community-based social support, and PrEP/HIV care and treatment data will be used in the analysis. Select demographic, clinic, and laboratory data (see Appendix 1) from these forms are entered routinely into OpenMRS (an electronic medical record “EMR” system) at FGH-supported sites. We will collect data about participant eligibility among those who attend ANC services including reasons for refusal among eligible participants. Lastly, we will assess PrEP drug levels using urine analysis (not considered standard of care) among participants in both groups (control and intervention).

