Contingency 10%	2,307	138,420		
TOTAL	25,377	1,522,620		

15. Timeline

Month	Activities/Description
Month 1	Hire personnel & train them in PrEP specific protocols and delivery of Storytelling intervention
Month 2-7	Recruit of discordant couples in ANC
Months 2-9	Delivery of storytelling intervention to couples
Months 2-9	Collect quantitative survey data at baseline and 3 months
Months 5-9	Collect qualitative data from intervention couples
Month 7	Coding and data analysis of qualitative data
Month 9-10	Conduct quantitative data analysis of survey data and adherence measures
Month 11-12	Write up R01 grant to conduct a larger healer-initiated counseling and testing project.
Months 11-12	Disseminate findings via community meetings in Zambézia, to the Ministry of Health in Maputo, and PEPFAR partners.

16. Statement of Conflict of Interest

As the Principal Investigator, I will be responsible for the relevance and quality of the project research, and for the confidentiality and anonymity of the participants.

Statement of conflict of interests

[figure not shown]
I, [name], as Principal Investigator of the Project entitled "*Partners-based HIV Treatment for Sero-concordant Couples attending Antenatal Care: Increasing family-based support for PrEP adherence among discordant couples through storytelling*", declare that I am an employee of the Vanderbilt University Medical Center in Nashville, Tennessee, USA, working closely with Friends in Global Health (FGH) in Mozambique.

I am engaged in the interview and survey design process, the evaluation design approach, as well as in the production of the pilot intervention and evaluation protocol. I will also contribute in the analysis and presentation of the results of the above-mentioned evaluation, in collaboration with:

- VUMC's Institute of Global Health: non-profit entity committed to building capacity in low-resource settings through interdisciplinary global health educational and training programs, technical assistance to government and civil sector organizations, and implementation science and research in order to improve health and equity.

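### The Section 15 timeline is one month short: couples enrolled in month 7 are due their 3-month survey in month 10, but survey collection ends at month 9

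*Combined protocol and SAP*

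**What the plan says.** All the dates are in Section 15 (Timeline) of the combined protocol and SAP:

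- Months 2-7: "Recruit of discordant couples in ANC".
- Months 2-9: "Collect quantitative survey data at baseline and 3 months".
- Months 9-10: "Conduct quantitative data analysis of survey data and adherence measures".
- Months 5-9: "Collect qualitative data from intervention couples".
- Month 7: "Coding and data analysis of qualitative data".

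The follow-up intervals are set elsewhere. Section 8a (Measurement of Results, Objective 1) lists the interviewer-assisted scales, ending with "motivation/perceived ability to adhere to medication[83] at baseline and three months". For the interviews, Section 8a states: "Qualitative interviews will be conducted at least 4 months after the couple and their indicated family members have been enrolled in the study". Section 7d gives the interview target: "Interviews will be conducted with 25-40 family members and 15-20 couples who participate in at least one storytelling session four months after enrollment". Section 7e continues enrolment until there are 70 couples. I found no visit window, no recruitment cut-off before month 7 and no later close for the surveys.

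**The concern.** Recruitment through month 7 plus a 3-month interval ends in month 10, while the survey row ends at month 9. If staff follow the table, couples enrolled in month 7 are never surveyed a second time.

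The Objective 1 endpoints (support, empathy, relationship satisfaction, knowledge, depression, motivation) come only from these surveys. A missed one cannot be rebuilt later from clinic records, as a pick-up date can. With 35 couples per arm there is little precision to spare. If staff instead survey late, the analysis slot opens while outcomes are still arriving, and the plan does not say when the data are final.

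The interview rows show a smaller mismatch of the same kind.

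**Working it through.** **The plan's own power figures.** Inputs from Section 7d: 35 women per arm, 5% type I error (two-sided assumed), non-retention 55% with RR 0.40 (so 22%), no detectable drug 70% with RR 0.50 (so 35%). Pooled two-proportion formula, with p̄ the mean of the two rates:

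power = Φ{[(p1 − p2) − 1.96·√(2p̄(1−p̄)/n)] / √[(p1(1−p1) + p2(1−p2))/n]}

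- 55% v 22%: 0.824, stated as 82%.
- 70% v 35%: 0.850, stated as 85%.

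Both reproduce.

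**When 3-month surveys fall due.** A couple enrolled in month m is due in month m + 3.

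| Enrolled in month | 3-month survey in month | Within survey row (to month 9)? |
|---|---|---|
| 2 | 5 | yes |
| 3 | 6 | yes |
| 4 | 7 | yes |
| 5 | 8 | yes |
| 6 | 9 | yes |
| 7 | 10 | no |

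**How many couples.** The documents give no accrual pattern, so this part is assumption. Put t = 0 at the start of month 1, so enrolment runs from t = 1 to t = 7. The share due by time t after follow-up f is u = (t − f − 1)/6 with even accrual, u² if the rate rises from zero, and 1 − (1 − u)² if it falls to zero. At the end of month 9 (t = 9, f = 3), u = 5/6:

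- Even accrual: 70 × (1 − 0.833) = 11.7 couples not yet due.
- Rising: 70 × (1 − 0.694) = 21.4.
- Falling: 70 × (1 − 0.972) = 1.9.

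If visits may be early by w months, the even-accrual figure is 70 × (1 − w)/6. One week (w = 0.25) gives 8.75, two weeks (w = 0.5) gives 5.8, and a full month gives 0.

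**Precision for Objective 1.** Losing 11.7 of 70 leaves about 29 couples per arm (35 × 5/6 = 29.2). For a two-sample t-test in one sex, two-sided 5%, 80% power, the detectable difference is 0.679 SD at 35 per arm and 0.749 SD at 29. The combined analysis of men and women in Section 10 would have its own detectable difference, but it should widen in about the same proportion: √(35/29) = 1.10.

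**Interviews.** The earliest couple (t = 1) reaches 4 months at t = 5, the start of month 6, so none can be due in month 5. By the end of month 9 (t = 9, f = 4), u = 4/6, and 35 × 4/6 = 23.3 intervention couples are due (15.6 to 31.1 from rising to falling accrual), against a target of 15-20. Coding is listed for month 7 alone, although collection continues to month 9.

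**The case against.** The table is a coarse administrative schedule in whole months. Month 7 may be a ceiling, since enrolment stops once 70 couples are in. Surveys are set per participant at three months, and nothing says that a couple is dropped or the database closed at month 9. Staff might well survey the last couples in month 10. This is fair as a prediction, but the document does not say it, and the survey row says otherwise.

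Other parts of the objection stand and limit the point:

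- A reader might infer that the timeline cannot deliver 3-month outcomes at all. Couples enrolled in months 2-6 fit it; only month-7 enrolments do not.
- A reader might count everyone short of 3 months when analysis opens at the start of month 9 (70 × 2/6, about 23 couples) as lost, and cut power to match. That needs a data freeze on that day, which the plan does not state. Its survey row runs on through month 9 and its analysis slot through month 10. Overlap is untidy but not a contradiction.
- A reader might infer that the 82% and 85% are overstated. Those figures concern retention and urine drug level, and Section 15 has no collection row for either. Retention comes from routine records, and the budget in Section 14 buys 210 urine tests, which is 70 × 3.
- A reader might infer that the interview target is out of reach. By month 9 the central figure of 23 couples exceeds it. Section 7d interviews to saturation, which is compatible with coding starting before collection ends.

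**Conclusion.** The rows conflict by one month, and the conflict is firm for the Objective 1 surveys of couples enrolled in month 7. Its size depends on accrual and visit tolerance, neither of which is stated: about 12 of 70 couples with even accrual and exact 3-month visits, 2 to 21 across the accrual patterns tried, and about 9 or 6 with one or two weeks of early tolerance. It disappears only if recruitment finishes by the start of month 7 or visits may be a full month early.

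Enrolment date should be unrelated to arm, so the loss should be similar in both arms and costs precision rather than causing bias. The step from 0.68 to 0.75 SD assumes 29 complete couples per arm and no other missing data. Retention and urine outcomes are affected only if data are cut before month 10 ends. The interview rows need tidying, but the documents do not show that interviews would be lost. This is a scheduling fault to correct before the trial starts, and it does not touch the design or the analysis model.

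**What to change.** Redraw Section 15 from the follow-up intervals:

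- Keep recruitment in months 2-7. Extend 3-month survey collection, and state the same for the month-3 urine assay, through the end of month 10, plus any visit window the sponsor sets.
- Lock the quantitative data, and start the final analysis, only after the last couple's 3-month contact.
- List interviews from month 6, and extend coding to the end of interview collection.

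The sample size and the power statements stay as they are. The cost is about one more month of the existing field staff, with analysis and write-up moving about one to two months later. No start date is given, so the fit with the September 2020 end date in Section 8c cannot be checked.

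Alternative: close recruitment at the end of month 6, so that the last 3-month survey falls by the end of month 9. This needs 70/5 = 14 couples a month instead of 70/6 = 11.7. The documents do not give the site's volume of eligible couples, so whether that rate is feasible is unknown. The final analysis would still have to wait for the end of month 9, which leaves one month of the present two-month slot.

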Appendix 1: List of Indicators/Data to Be Collected

[figure not shown]
Demographics data (to be obtained from study registry documents and OpenMRS database)

1. Number of couples attending ANC
2. Number of couples eligible for study (female HIV-negative/ male HIV-positive)
3. Reasons for couples refusing entry into the study

4. District;
5. Health facility;
6. Urban (yes/no);
7. Main (**sede**) health facility (yes/no);
8. NID;
9. Sex;
10. Date of birth;
11. Age (years), at current enrollment;
12. Employment status at the time of enrollment;
13. Marital status of the patient at time of enrollment;
14. Sexual preference/orientation at time of enrollment;
15. Village, town, or city of residence at PrEP/ART initiation;
16. Previous ART enrollment (yes/no) (Male partner);
17. Previous ARV regimen before patient was LTFU (if applicable);
18. ART regimen at re-initiation/initiation (current medication regimen);
19. Enrollment date (current);
20. PrEP/ART initiation date (current);
21. WHO clinical stage at ART initiation, and date of documentation (male partner);
22. CD4+ cell count (cells/mm³) 'at enrollment', taken between enrollment and 1 month after enrollment, and date of sample collection (male partner);
23. All CD4+ cell counts (cells/mm³) and dates of sample collections (male partner);
24. Viral load, first result obtained at or after enrollment, and results of any other VL tests, and date of sample collection (male partner);

25. All previous TB investigation results (positive/negative), and date of investigation (male partner);
26. Previous date of enrollment in TB services (if applicable) (male partner);
27. Previous TB treatment completed (yes/no) (if applicable) (male partner);
28. Previous date TB treatment completed (if applicable) (male partner);
29. Current enrollment in TB services, at (ART) enrollment, and date of documentation (male partner);
30. Weight (kg), at enrollment, and at all other clinic visits, and date of documentation;
31. Height (m²), at enrollment, and date of documentation;
32. Body mass index (kg/m²) at enrollment, and at all other clinic visits, and date of documentation;
33. Hemoglobin, at enrollment, and at all other clinic visits, and date of documentation;
34. Blood pressure, at enrollment, and at all other clinic visits, and date of documentation;
35. Alanine Transferase (ALT) at enrollment, at PrEP/ART initiation, and date of documentation;
36. Creatinine at enrollment, at ART initiation, and date of documentation;
37. Patient status (active, default, LTFU, transfer, or death) every month after enrollment;
38. Dates of all PrEP/ART pick-ups
39. Dates of all next scheduled PrEP/ART pick-ups;
40. Dates of all clinic visits
41. Dates of all next scheduled clinic visits;
42. Date cotrimoxazole (CTX) prescribed;
43. Patient reported use of intravenous (IV) drugs;
44. Patient reported use of tobacco;
45. Patient reported use of alcohol;
46. Estimated due date of pregnant female patient;
47. Initiation of any family planning method (Depo, pill, intrauterine device (IUD), implant, condoms, lactational amenorrhea [LAM], tubal ligation, vasectomy [male partner]), and date of initiation;
48. Continuation of any family planning method (Depo, pill, IUD, implant, condoms, LAM, tubal ligation), and date of continuation;
49. Final patient outcome status and date of final status:
 - a. Transfer out of care at that facility, and date of transfer out;
 - b. Death, date of death recorded, cause of death where available;
 - c. LTFU, date of most recent visit (LTFU defined as not returning for >60 days past last scheduled appointment / pick-up date);

- 50. Number of babies with this pregnancy;
- 51. Concentration of PrEP in patient urine;
- 52. Monthly patient self-report of adherence using this scale:

(for each baby, if multiple live births this pregnancy)

- 53. Date of birth of infant(s);
- 54. Infant status at birth (alive, dead);
- 55. Sex of infant(s);
- 56. Weight of infant(s) at birth, and at all other clinic visits, and date of documentation;
- 57. Whether infant(s) received ART prophylaxis after birth, date of start, and type of ARV;
- 58. Data on infant feeding practices where available;
- 59. Date of any PCR testing for infant(s), and test results;
- 60. Date of any HIV rapid testing for infant(s), and test results;
- 61. Data on discharge from CCR services (transfers, referrals, abandoned, died), and date;
- 62. Health status of child(ren) at 18 months (alive, dead);
- 63. HIV health status of child(ren) at 18 months (HIV-positive, HIV-negative)

ANC-specific indicators (aggregated data, from OpenMRS and DHIS databases)

- 64. Number of pregnant women who arrived for first ANC appointment;
- 65. Number of pregnant women who know their serostatus, known positive;
- 66. Number of pregnant women who know their serostatus, recently tested;
- 67. Number of pregnant women who received HIV test results in ANC, first test (positive, negative, and indeterminate results);
- 68. Number of pregnant women who received HIV test results in ANC, repeat test, positive, negative, and indeterminate results);
- 69. Number of HIV-positive pregnant women enrolled in ANC;

70. Number of HIV-positive pregnant women who received ARVs to reduce risk of MTCT (NVP, AZT+NVP, initiated ART, and already on ART);
71. Number of pregnant women receiving CTZ upon entrance to ANC;
72. Number of HIV-positive pregnant women that initiate prophylaxis with CTZ;
73. Number of HIV-positive pregnant women who are clinically malnourished (DAM, DAG);
74. Number of HIV-positive pregnant women who receive nutritional support (supplemental and therapeutic);
75. Number of HIV-negative pregnant women who receive nutritional support (supplemental and therapeutic);
76. Number of pregnant women in ANC with HIV-negative results;
77. Number of partners of pregnant women present in ANC;
78. Number of partners of pregnant women who tested for HIV in ANC;
79. Number of partners of pregnant women who tested for HIV in ANC and received results, by test result (positive, negative, or indeterminate);
80. Number of HIV-positive partners of pregnant women who initiated ART in ANC.

Appendix 2: Storytelling Intervention

The three motivational stories include the following themes:

- (1) A couple who has to overcome the difficulties associated with having a different HIV status compared to their partner. Specifically, how they address accusations of infidelity, how they manage to take different medications, interpret different messages (lifelong ART vs. short term PrEP), and a woman's concerns with seroconversion. How their family provides emotional and physical support via assistance in food preparation, completing chores around the house, and counseling both partners not to give up on the medication.
- (2) A woman who overcomes the difficulties of an unsupportive husband and extended family. The story of a woman who wants to take PrEP but must take medication and attend clinical visits without detection. The challenges she encounters while hiding her treatment, the moment of discovery, and how she successfully changes the beliefs and attitudes of her husband and extended family.
- (3) An encouraging couple who overcomes the difficulties of an unsupportive extended family. The story of a couple who support each other in medication adherence but face the scorn and derision of their extended family. The extended family blames the man for exposing the pregnant woman and her unborn child to HIV. The strategies this couple uses to change the attitudes and options of their family, to remain adherent to medication, and to have an HIV-uninfected baby.

Appendix 3: Measures used in study

1. Social Support (Berlin Social Support Scales)

Perceived Emotional Support

1. There are some people who truly like me.
2. Whenever I am not feeling well, other people show me that they are fond of me.
3. Whenever I am sad, there are people who cheer me up.
4. There is always someone there for me when I need comforting.

Perceived Instrumental Support

1. I know some people upon whom I can always rely.
2. When I am worried, there is someone who helps me.
3. There are people who offer me help when I need it.
4. When everything becomes too much for me to handle, others are there to help me.

Need for Support

1. When I am down, I need someone who boosts my spirits.

2. It is important for me always to have someone who listens to me.
3. Before making any important decisions, I absolutely need a second opinion.
4. I get along best without any outside help. (-)

Support Seeking

1. In critical situations, I prefer to ask others for their advice.
2. Whenever I am down, I look for someone to cheer me up again.
3. When I am worried, I reach out to someone to talk to.
4. If I do not know how to handle a situation, I ask others what they would do.
5. Whenever I need help, I ask for it.

2. Relationship Empathy (Davis; Interpersonal Reactivity Index [IRI])

1. I daydream and fantasize, with some regularity, about things that might happen to me.
2. I often have tender, concerned feelings for people less fortunate than me.
3. I sometimes find it difficult to see things from the "other guy's" point of view.
4. Sometimes I don't feel very sorry for other people when they are having problems.
5. I really get involved with the feelings of the characters in a novel.
6. In emergency situations, I feel apprehensive and ill-at-ease.
7. I am usually objective when I watch a movie or play, and I don't often get completely caught up in it.
8. I try to look at everybody's side of a disagreement before I make a decision.
9. When I see someone being taken advantage of, I feel kind of protective towards them.
10. I sometimes feel helpless when I am in the middle of a very emotional situation.
11. I sometimes try to understand my friends better by imagining how things look from their perspective.
12. Becoming extremely involved in a good book or movie is somewhat rare for me.
13. When I see someone get hurt, I tend to remain calm.
14. Other people's misfortunes do not usually disturb me a great deal.
15. If I'm sure I'm right about something, I don't waste much time listening to other people's arguments.

16. After seeing a play or movie, I have felt as though I were one of the characters.
17. Being in a tense emotional situation scares me.
18. When I see someone being treated unfairly, I sometimes don't feel very much pity for them.
19. I am usually pretty effective in dealing with emergencies.
20. I am often quite touched by things that I see happen.
21. I believe that there are two sides to every question and try to look at them both.
22. I would describe myself as a pretty soft-hearted person.
23. When I watch a good movie, I can very easily put myself in the place of a leading character.
24. I tend to lose control during emergencies.
25. When I'm upset at someone, I usually try to "put myself in his shoes" for a while.
26. When I am reading an interesting story or novel, I imagine how I would feel if the events in the story were happening to me.
27. When I see someone who badly needs help in an emergency, I go to pieces.
28. Before criticizing somebody, I try to imagine how I would feel if I were in their place.

3. Patient Health Questionnaire - 9 (PHQ-9 Depression Screening tool)

Over the last 2 weeks, how often have you been bothered by any of the following problems?

1. Little interest or pleasure in doing things.
2. Feeling down, depressed, or hopeless.
3. Trouble falling or staying asleep or sleeping too much.
4. Feeling tired or having little energy.
5. Poor appetite or overeating.
6. Feeling bad about yourself - or that you are a failure or have let yourself or your family down.
7. Trouble concentrating on things, such as reading the newspaper or watching television.
8. Moving or speaking so slowly that other people could have noticed? Or the opposite – being so fidgety or restless that you have been moving around a lot more than usual.
9. Thoughts that you would be better off dead or of hurting yourself in some way.

4. Relationship Satisfaction:

1. How well does your partner meet your needs?
2. In general, how satisfied are you with your relationship?
3. How good is your relationship compared to most?
4. How often do you wish you hadn't gotten into this relationship?
5. To what extent has your relationship met your original expectations?
6. How much do you love your partner?
7. How many problems are there in your relationship?

5. Self-Efficacy Beliefs

"I believe that I can

1. Keep a clinic appointment
2. Follow overall treatment regimen
3. Follow a plan for taking PrEP medication
4. Take my PrEP Medication with correct intervals
5. Take correct dose of my medications
6. take my medications while I am at the farm
7. Take my medications on a weekday
8. Take my medications on a weekend
9. Take my medications if I am travelling
10. Take my medications even if I feel well
11. Take my medications even if I feel ill
12. Take my medications even if I am having medication side effects
13. Take my medications even if I am having a personal crisis

6. Outcome Expectancy

If I take my PrEP medication regularly I will....

1. be healthy
2. have a good quality of life
3. have a long life
4. lead a normal life
5. avoid getting HIV

